8.5 Pharmacokinetics

- Blood samples of approximately 6 mL will be collected for measurement of plasma concentrations of BUP and norbuprenorphine at times points specified in the SoE.
- Additional samples may be collected for participants who experience an SAE. Samples should be collected as soon as the investigator is made aware of the SAE and additional blood samples may be collected, after a period of time, to confirm resolution of the SAE.
- Instructions for the collection and handling of samples will be provided by the sponsor. The actual date and time (24-hour clock time) of each sample will be recorded. Briefly, blood will be collected in a pre-labelled 6-mL K₂EDTA vacutainer tube by individual venipuncture. Blood samples will be centrifuged and the plasma will be transferred into 2 aliquots of approximately 1.5 mL each in pre-labelled polypropylene tubes. Plasma samples will be stored at -20°C until analysis.
- The plasma concentration of BUP and norbuprenorphine will be quantified using a previously validated liquid chromatography tandem mass spectroscopy method.

8.6 Pharmacodynamics

Not applicable

8.7 Genetics

Genetics are not evaluated in this study.

8.8 Biomarkers

Biomarkers are not evaluated in this study.

8.9 Health Economics

Health economics parameters are not evaluated in this study.

Confidential 44 of 64

9 STATISTICAL CONSIDERATIONS

The statistical analysis plan will be finalised prior to database lock and it will include a more technical and detailed description of the statistical analyses described in this section. This section is a summary of the planned statistical analyses of the most important endpoints including primary and key secondary endpoints.

9.1 Statistical Hypotheses

No formal statistical hypotheses will be tested in this study. Relative bioavailability of BUP when administered to alternative injection sites (back of upper arm, buttocks, and thigh) compared to that when administered to the abdomen will be informally evaluated.

9.1.1 Multiplicity Adjustment

Not applicable for this study.

9.2 Analyses Sets

For purposes of analysis, the following populations are defined:

Table 6 Populations for Analysis

Population	Description	
Screened	All participants who sign the ICF.	
Enroled	All screened participants who received the first dose of SUBOXONE film during run-in.	
Randomised	All enroled participants who are randomised to one of the 4 treatment arms (injection locations).	
PK Analysis Set	All randomised participants who receive SUBLOCADE injection and provide at least 1 PK sample post randomisation. The participants will be analysed corresponding to the injection location used.	
PK Evaluable Analysis Set	All randomised participants who receive SUBLOCADE injection and provide an adequate number of post randomisation PK samples to derive key PK parameters for SUBLOCADE (ie, C _{max} , and AUC _{0-28days}). The participants will be analysed corresponding to the injection location used.	
Safety Analysis Set	All enroled participants who received SUBLOCADE injection. The participants will be analysed corresponding to the injection location used.	
Run-In Safety Analysis Set	All enroled participants who receive at least 1 dose of SUBOXONE film during run-in.	

Confidential 45 of 64

9.3 Statistical Analyses

9.3.1 General Considerations

Continuous variables will be summarised using descriptive statistics such as mean, SD, median, interquartile range, minimum, and maximum. Categorical variables will be reported as frequency counts (including number missing) and the percentage of participants in corresponding categories.

BUP and norbuprenorphine plasma concentrations following SUBLOCADE injection will be summarised at each scheduled time point by injection location using the PK Analysis set. BUP and norbuprenorphine plasma concentrations during run-in with SUBOXONE film will also be summarised at each scheduled time point using the Enroled participant set for participants who have at least 1 PK sample post SUBOXONE dose. Concentrations that are below the lower limit of quantification (BLQ) will be treated as zero for the summary statistics. Mean BUP and norbuprenorphine plasma concentration-time curves will be presented for the Run-in Period with SUBOXONE film for overall and for SUBLOCADE phase stratified by injection locations.

Details for handling missing and aberrant plasma concentrations for deriving BUP and norbuprenorphine PK parameters will be detailed in the SAP.

9.3.2 Primary Analysis

9.3.2.1 Definition of Endpoints

The primary PK parameters of BUP following SUBLOCADE injection will be derived as shown in Table 7 using the PK evaluable set. Calculations will be done by noncompartmental analysis using WinNonlin Phoenix version 6.3 or higher.

Table 7 Primary PK Parameters of BUP following SUBLOCADE injection

AUC _{0-28days}	Area under the concentration-time curve from study Day 1 to Day 29 of BUP, calculated by the linear trapezoidal method
C _{max}	Maximum observed plasma concentration of BUP

9.3.2.2 Main Analytical Approach

Natural log-transformed $AUC_{0-28days}$ and C_{max} from SUBLOCADE Phase for BUP will be analysed using an ANOVA model with injection site location as the independent variable. The 90% CI will be estimated for the ratio of population geometric means (test/reference) corresponding to exponentiated differences in least square means.

The comparisons of interest are the 3 alternative injection sites (test) versus abdomen (reference, namely: back of upper arm vs abdomen, buttocks vs abdomen, and thigh vs abdomen.)

Confidential 46 of 64

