Participants will provide written informed consent before any protocol-related procedures commence. The study includes both a Residential (Inpatient) Period and a Non-Residential (Outpatient) Period.

Following Screening, all eligible participants must be stabilised on 12 mg SUBOXONE® (BUP/naloxone) sublingual film QD for a minimum of 7 days before the SUBLOCADE injection. Dose induction/stabilisation onto SUBOXONE may be completed as outpatient or inpatient, as necessary, according to the prescribing information for a maximum of 14 days before SUBLOCADE injection.

All participants will be admitted to the residential facility by the evening of Day -3.

The period from the first dose of SUBOXONE administered as part of this study through Day -1 will be referred to as the Run-in Period.

Following the Run-in Period, on Day 1, eligible participants will be randomised to a treatment arm.

Each treatment arm will receive a single, SC injection of 300 mg SUBLOCADE at a different injection location ie, abdomen (reference) or 1 of the alternative injection locations (test) ie, back of upper arm, buttocks, and thigh.

Safety measurements and blood samples for PK assessments during the Residential Period will be collected at scheduled time points until the participants are discharged from the residential facility on Day 3.

Participants will return to the clinical facility as outpatients for safety and PK assessments to be conducted according to the SoE until EOT.

Any participant with ongoing AEs at the EOT or ET visit will also be followed up by phone 2 weeks later for the EOS visit to assess any ongoing AEs and concomitant medications associated with those ongoing AEs only.

It is important that participants do not use any BUP-containing products, either therapeutically or illicitly during the course of the study. Such use would compromise the PK assessment of BUP and its metabolite, norbuprenorphine.

Number of Participants:

No formal statistical power analysis was performed to determine the sample size of this study. Based on historical experience from previous similar clinical trials, approximately 80 participants will be randomised in total, ideally to achieve 15 PK evaluable participants per each of the 4 treatment arms (injection locations): abdomen (reference), back of upper arm, buttocks, and thigh.

CONFIDENTIAL 12 of 64

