3 OBJECTIVES AND ENDPOINTS

Table 4 Objectives and Endpoints

Objective		Corresponding Endpoint		
Primary				
•	To assess the relative bioavailability of BUP when administered at alternative injection locations (test treatments), in comparison to the abdomen (reference treatment) following a single SC injection of SUBLOCADE in participants with OUD	AUC _{0-28days} and C _{max} for BUP		
Secondary				
•	To evaluate the safety and tolerability of SUBLOCADE when administered at alternative injection locations, in comparison to the abdomen	 Proportion of participants with TEAEs Proportion of participants with TEAEs		
Exploratory				
•	To assess other BUP PK parameters To assess the relative bioavailability of norbuprenorphine	 AUC_{last}, T_{max}, and C_{trough} for BUP AUC_{0-28days}, AUC_{last}, and C_{max} for norbuprenorphine 		
•	To assess other norbuprenorphine PK parameters	T _{max} and C _{trough} for norbuprenorphine		

AUC=area under the curve; BUP=buprenorphine; C_{max} =maximum plasma concentration; C_{trough} =trough plasma concentration measured on Day 29; OUD=opioid use disorder; SAE=serious adverse event; SC=subcutaneous; TEAE=treatment-emergent adverse event; T_{max} =time to maximum plasma concentration; VAS=visual analogue scale

The primary clinical question of interest is the following: Is the bioavailability of BUP when SUBLOCADE is administered in the back of upper arm, buttocks, and thigh similar to that when administered in the currently approved location, the abdomen?

Confidential 21 of 64

The estimand for the primary endpoints is described by the following attributes:

- Estimand strategy: While on treatment strategy.
- Population: PK evaluable population (see Table 6).
- Endpoints: AUC_{0-28 days} and C_{max} of BUP.
- Treatment condition: Administration of SUBLOCADE to 1 of the randomised injection site locations.
- Remaining intercurrent events: There are no other intercurrent events anticipated at this time.
- Population-level summary: The ratio of geometric means and corresponding 90% CI for each alternative injection site vs the reference site (abdomen).

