5.3 Randomisation Criteria

- 1. Females of reproductive potential must have a negative urine pregnancy test on Day -3.
- 2. Dose-stabilised on 12 mg QD of SUBOXONE sublingual film for a minimum of 7 days (last dose on the morning of Day -1).

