9.3.4 Exploratory Endpoint Analyses

The following PK parameters for SUBLOCADE will be derived as shown in Table 8 for BUP and Table 9 for norbuprenorphine using the PK Evaluable Analysis Set. Calculations will be done by noncompartmental analysis using WinNonlin Phoenix. The plasma terminal half-life and AUC extrapolated to infinity (AUC_{0-inf}) are not calculated as the duration of the PK evaluation is shorter than the half-life reported for SUBLOCADE (43-60 days).

Table 8 Additional PK Parameters of BUP Following SUBLOCADE Injection

AUC _{last}	Area under the concentration-time curve from time 0 to the last quantifiable BUP concentration, calculated by the linear trapezoidal method
T _{max}	Time to attain the maximum observed BUP plasma concentration
C _{trough}	Trough BUP plasma concentration measured on Day 29

Confidential 47 of 64

Table 9 PK Parameters of Norbuprenorphine Following SUBLOCADE Injection

AUC _{0-28days}	Area under the concentration-time curve from Study Day 1 to Day 29 of norbuprenorphine, calculated by the linear trapezoidal method
AUC _{last}	Area under the concentration-time curve from time 0 to the last quantifiable concentration of norbuprenorphine, calculated by the linear trapezoidal method
C _{max}	Maximum observed norbuprenorphine plasma concentration
T _{max}	Time to attain the maximum observed norbuprenorphine plasma concentration
C _{trough}	Trough norbuprenorphine plasma concentration measured on Day 29

 AUC_{last} for both analytes, and $AUC_{0-28days}$ and C_{max} for norbuprenorphine will be analysed using the same statistical ANOVA model as described in Section 9.3.2.

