10.5 Appendix 5: Prohibited Concomitant Therapies

Medications prohibited during the study include, but are not limited to, the following:

Cytochrome P450 3A4 Inhibitors		Cytochrome P450 3A4 Inducers	Cytochrome P450 2C8 Inhibitors	Cytochrome P450 2C8 Inducers
Amiodarone	Ketoconazole	Barbiturates	Gemfibrozil	Rifampicin
Amprenavir	Metronidazole	Carbamazepine	Trimethoprim	
Aprepitant	Mibefradil	Dexamethasone	Glitazones	
Chloramphenicol	Miconazole	Efavirenz	Montelukast	
Cimetidine	Mifepristone	Ethosuximide	Quercetin	
Ciprofloxacin	Nefazodone	Glucocorticoids		
Clarithromycin	Nelfinavir	Glutethimide		
Clotrimazole	Nicardipine	Modafinil		
Cyclosporine	Norfloxacin	Nevirapine		
Delavirdine	Norfluoxetine	Oxcarbazepine		
Diethyl- dithiocarbamate	Propofol	Phenobarbital		
Diltiazem	Quinine	Phenytoin		
Ethinyl estradiol	Ritonavir	Pioglitazone		
Erythromycin	Saquinavir	Primidone		
Fluconazole	Sertraline	Rifabutin		
Fluoxetine	Starfruit	Rifampin		
Fluvoxamine	Telithromycin	Hypericum perforatum		
Gestodene	Troleandomycin	Sulfadimidine		
Grapefruit juice	Verapamil	Sulfinpyrazone		
Imatinib	Voriconazole	Troglitazone		
Indinavir	Zafirlukast	Troleandomycin		
Itraconazole		a/ddis/clinical-table/	124 1 1 2217	

Source: http://medicine.iupui.edu/clinpharm/ddis/clinical-table/. Accessed 31 July 2015.

Confidential 60 of 64

10.6 Appendix 6: Schedule of Assessments – Day -3 to Day 3

Table 11 Schedule of Events – Detailed Inpatient Day -3 to Day 3 With Assessment Windows

Assessment Window	Assessment		
Day -3			
Prior to vital signs and clinical laboratory assessments	12-lead ECG		
After 12-lead ECG	Vital signs		
After 12-lead ECG	Liver function assessment		
After 12-lead ECG	Urine pregnancy test		
Do	ру -2		
≤15 minutes prior to SUBOXONE dose	PK sample		
0 hour	SUBOXONE dose		
Day -1			
≤15 minutes prior to SUBOXONE dose	PK sample		
0 hour	SUBOXONE dose		
+30 minutes (±5 minutes)	PK sample		
+1 hour (±5 minutes)	PK sample		
+2 hours (±5 minutes)	PK sample		
+4 hours (±5 minutes)	PK sample		
+6 hours (±15 minutes)	PK sample		
+12 hours (±15 minutes)	PK sample		
Days 1 to 3			
Pre-Dose SUBLOCADE			
Prior to SUBLOCADE injection	Randomisation criteria reviewed and randomisation		
≤60 minutes prior to SUBLOCADE injection	Vital signs		
≤30 minutes prior to SUBLOCADE injection	PK sample		

Confidential 61 of 64

Assessment Window	Assessment		
0 hour	300 mg SUBLOCADE administration		
+1 minute (±1 minute)	Injection Site Pain VAS		
+5 minutes (±2 minutes)	Injection Site Pain VAS		

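### The primary ANOVA is valid but makes no inferential use of the pre-randomisation Day -1 buprenorphine profile; its 90% CIs are wider than needed, on average, if run-in and post-injection exposure correlate above about 0.14.

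*Protocol*

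**What the plan says.** Section 9.3.2.2 of the protocol states that the log-transformed primary endpoints "will be analysed using an ANOVA model with injection site location as the independent variable", and takes 90% CIs for the three test/abdomen ratios from it. Section 9.3.4 extends the model: AUClast for both analytes, and AUC0-28days and Cmax "for norbuprenorphine will be analysed using the same statistical ANOVA model as described in Section 9.3.2".

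The estimand in section 3 makes the geometric mean ratio with its 90% CI the population-level summary. Under section 9.1 there is no hypothesis test, and bioavailability at the alternative sites "compared to that when administered to the abdomen will be informally evaluated".

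On the run-in, section 5.3 requires at least 7 days of stable dosing on 12 mg SUBOXONE once daily, with the last dose on the morning of Day -1. Appendix 10.6 (Table 11) schedules Day -1 PK samples before that dose and at 0.5, 1, 2, 4, 6 and 12 hours after it. The synopsis then says: "Following the Run-in Period, on Day 1, eligible participants will be randomised to a treatment arm". The only stated use of the run-in data is in section 9.3.1: "BUP and norbuprenorphine plasma concentrations during run-in with SUBOXONE film will also be summarised at each scheduled time point", together with mean concentration-time curves.

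Section 9 describes itself as a summary, with technical detail left to the SAP. Of the SAP, only an addendum dated 19 March 2024 is available. It deals with concomitant-medication flags.

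**The concern.** The design is parallel-group with a target of 15 PK-evaluable participants per arm, so between-participant variance sets the width of every primary interval. With no margin, test or power calculation, that width is the main measure of how much the study can say about similarity.

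The Day -1 samples give an AUC0-12h of the same analyte, in the same person, on a common dose, and injection location cannot affect it. A baseline variable of this kind can remove some between-participant variance without biasing the comparison. The primary model leaves it out. If run-in exposure predicts depot exposure to a useful degree, the reported intervals will be wider than the scheduled data allow.

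**Working it through.** **Inputs from the protocol.** Four arms, 15 evaluable per arm (synopsis; section 9.5), so N = 60. Error df are 56 for the ANOVA and 55 with one covariate. Intervals are two-sided 90%.

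**Assumptions, because the documents give no figure.** Rho between ln run-in AUC and each ln endpoint is taken from 0 to 0.7, to be read separately for AUC0-28days and Cmax. A CV is needed only for absolute intervals; it cancels from the width ratio. The protocol has no power calculation to reproduce.

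**Step 1: ANOVA interval.** Log-scale half-width = t(0.95, 56) × sqrt(ln(1 + CV²)) × sqrt(2/15). At an assumed CV of 40% and a ratio of 1.0: 1.6725 × 0.3853 × 0.3651 = 0.2353, giving 0.790–1.265. At CV 30% it is 0.836–1.196, and at CV 50% it is 0.749–1.334.

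**Step 2: effect of the covariate.** The residual variance is multiplied by (1 − rho²). Chance imbalance in a normal covariate inflates the variance of a contrast by (56 − 1)/(56 − 2) = 1 + 1/54 on average, and the t quantile rises by a factor of 1.6730/1.6725 = 1.0003.

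Mean width ratio (ANCOVA/ANOVA) = 1.0003 × sqrt[(1 − rho²)(1 + 1/54)].

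| rho | Mean width ratio | 5th–95th percentile per contrast | Contrasts wider under ANCOVA | CI at CV 40%, ratio 1.0 |
|---|---|---|---|---|
| 0 | 1.009 | 0.980–1.039 | 80% | 0.789–1.268 |
| 0.2 | 0.989 | 0.930–1.030 | 44% | 0.792–1.262 |
| 0.3 | 0.963 | 0.886–1.018 | 19% | 0.797–1.254 |
| 0.5 | 0.874 | 0.772–0.968 | 1% | 0.814–1.228 |
| 0.7 | 0.721 | 0.610–0.838 | 0% | 0.844–1.185 |

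The percentiles and shares come from simulation (400,000 trials of 4 × 15 per rho). Coverage was 0.899–0.901 for both models.

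**Step 3: break-even.** Set the ratio to 1: rho = sqrt(1 − 1/[1.0003² × (1 + 1/54)]) = 0.137. By the same formula it is 0.173 at 10 per arm and 0.117 at 20 per arm.

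**Step 4: downside if rho is 0.** 45% of contrasts are more than 1% wider and 5% are at least 3.9% wider. The widest of a trial's three contrasts averages 1.8% wider (95th percentile 5.4%). At 10 per arm the mean is 1.5% wider (95th percentile 6.2%).

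**Step 5: missing run-in samples.** Treat AUC0-12h as missing if the pre-dose or 12 h sample is absent, or if two or more of the five between them are. With a fraction p of samples lost at random and q = 1 − p, the missing rate is 1 − q²(q⁵ + 5pq⁴): 11.8% at p = 5% and 25.6% at p = 10%. Filling in the all-arm mean gives width ratios of 1.009, 0.969, 0.892 and 0.762 (5% lost), or 1.009, 0.975, 0.912 and 0.807 (10% lost), at rho 0, 0.3, 0.5 and 0.7. Coverage stays at 0.899–0.901.

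**Step 6: robustness.** Arms of 12/15/18/15 and t(5) errors leave coverage at 0.900–0.901. Slopes that differ by arm, at equal total variance, do move ANCOVA coverage:

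- abdomen 0.7 against 0.3/0.5/0.5: 0.899–0.922
- abdomen 0.3 against 0.7/0.5/0.5: 0.878–0.899
- extreme case, abdomen 0 against 0.7 in all others: 0.858–0.859

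ANOVA coverage is 0.900–0.901 in all three.

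**The case against.** The strongest reply is that a one-factor model is a legitimate choice and no loss has been shown. Everything turns on rho, which the documents never give. Run-in exposure follows a sublingual film, while the endpoints follow a subcutaneous depot over 28 days; shared clearance makes some correlation plausible but does not show that it reaches 0.3 to 0.5. Near the threshold there is nothing to gain: in a simulation at rho 0.14, 60% of contrasts were wider under ANCOVA, and most contrasts narrow only above about 0.18. No margin or test depends on the width. The remedy also assumes a common slope across four anatomical sites and adds a derived parameter, a missing-data rule and an imputation. The full SAP may already contain an adjustment, and the database is locked.

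Most of this stands as a limit on the claim. Break-even is where adjustment stops costing, not where it becomes worthwhile; a material gain needs rho of about 0.3 or more. The slope risk is real and is the reason to keep the ANOVA. The point can be made only about the protocol text. None of this shows the point to be wrong. The 90% CI is the study's stated summary, which makes its width matter more when there is no formal criterion. The exchange is also lopsided: about 1% of width on average if rho is 0, against 13% at rho 0.5, where matching the gain by recruitment would take about 1/0.874² = 1.31 times as many participants per arm.

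**Conclusion.** The point holds as a conditional one about precision. The protocol's ANOVA is unbiased and has correct coverage under equal variances, and no stated figure is wrong. At 15 evaluable per arm, leaving out the Day -1 profile costs width on average if rho exceeds 0.137: little at 0.2 (1%), modest at 0.3 (4%), substantial at 0.5 (13%) and 0.7 (28%). Below break-even the ANOVA is slightly the better choice. These figures assume a normal covariate, a common slope and equal arms of 15; rho is unknown and may differ between AUC0-28days and Cmax. Adjustment should have been pre-specified as a cheap improvement. Confidence is medium, because rho is not given and the full SAP was not available.

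**What to change.** **Change to section 9.3.2.2.** Pre-specify an ANCOVA of ln AUC0-28days and ln Cmax for BUP on injection location plus ln Day -1 BUP AUC0-12h (linear trapezoidal, pre-dose to 12 h). Apply the missing rule in step 5, with a single interior gap bridged by the trapezoid, and set a missing ln AUC0-12h to the all-arm mean so that nobody leaves the PK Evaluable Analysis Set. Keep the location-only ANOVA as a sensitivity analysis, since its coverage does not depend on a common slope.

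**Change to section 9.3.4.** State that the exploratory models stay location-only or, for norbuprenorphine, use its own run-in AUC0-12h. Otherwise the cross-reference to section 9.3.2 carries the BUP covariate into them.

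**Timing.** The SAP addendum shows that the database is locked. If the full SAP has no such covariate, leave the ANOVA as primary and report the ANCOVA as a labelled post hoc sensitivity analysis.

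**Cost.** No new samples. One derived parameter not now in Tables 7 to 9 (two if norbuprenorphine is adjusted for its own), one sentence in 9.3.4, and one error df. If rho is 0, intervals are about 1% wider on average, with 1 contrast in 20 about 4% wider or more. If slopes differ by arm, ANCOVA coverage can move off 90%.

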9.3.3 Secondary Endpoint Analysis

All secondary endpoints summaries will be based on the Safety Population.

The following secondary endpoints will be derived as the proportion of participants reporting at least one of the specified events, and summarised using frequency counts and percentages:

- Proportion of participants with TEAEs
- Proportion of participants with TEAEs identified as injection site reactions
- Proportion of participants with treatment-emergent SAEs

TEAEs identified as injection site reactions will be summarised using customised MedDRA queries. Details of the customised MedDRA queries will be provided in the SAP.

Each component of the Injection site grading (induration, swelling, pain, tenderness and erythema) at 10 minutes and 2 hours post SUBLOCADE dosing will be summarised using frequency counts and percentages of participants reporting the specific level of severity.

Injection Site Pain VAS at 1, 5, 10, 15, and 30 minutes post SUBLOCADE dosing will be summarised using descriptive statistics.

All summaries will be by the injection site anatomical location and overall. No hypotheses testing will be performed to compare the injection site locations.

